Evaluation of the Treatment of Multiple Gingival Recession Using Modified Coronally Advanced Tunnel With Subepithelial Connective Tissue Graft Depending on the Positioning of the Graft

NCT06366022

04/10/2024

Current State of Knowledge

Thanks to the modified tunnel technique using an autogenous subepithelial connective tissue graft, we can effectively treat gingival recessions. [1] This surgical approach ensures minimal postoperative discomfort for patients, among other reasons due to minimizing vertical incisions and preserving the integrity of the interdental papilla. The material considered the gold standard in root coverage procedures is an autogenous connective tissue graft. [2] One method of harvesting it is de-epithelialization of a free gingival graft (FGG).

Purpose of the study

The aim of the present study is to compare the outcomes of a modified tunnel technique with an autogenous subepithelial connective tissue graft in gingival recessions, depending on whether the graft is positioned with its inner surface (previously adjacent to the periosteum) facing the covering flap versus its outer surface facing the covering flap.

Description of the study

- **Type of study:** randomized split-mouth interventional study.
- **Sample size:** 20 test sites and 20 control sites (20 patients)
 - a. **Inclusion criteria:**
 - I. Adult patients aged 18 to 60 years
 - II. Generally healthy patients or patients with controlled systemic diseases
 - III. Presence of multiple gingival recessions
 - b. **Exclusion criteria:**
 - I. Plaque index $\geq 20\%$ (Ainamo & Bay 1975)
 - II. Bleeding index $\geq 15\%$ (Mühlemann & Son 1971)
 - III. Tobacco smoking
 - IV. Uncontrolled systemic diseases with potential impact on tissue healing
 - V. Use of medications affecting healing (cytostatics, corticosteroids)
 - VI. Pregnant or breastfeeding women
- **Study endpoints:**
 - I. **Primary endpoint** – gingival recession/root coverage.
 - II. **Secondary endpoints** – gingival thickness, width of keratinized gingiva.

- **Procedure description:**

After obtaining written informed consent, the following periodontal parameters will be assessed: probing depth, height and width of gingival recession, gingival thickness (1 mm from the gingival margin), and width of keratinized gingiva. Then, under local anesthesia, root coverage surgery will be performed using a modified tunnel technique with an autogenous subepithelial connective tissue graft (sCTG). On the test side, the graft will be positioned with its inner surface (previously adjacent to the periosteum) facing the flap covering the graft, whereas on the control side the graft will be positioned with its outer surface facing the flap covering the graft. (Allocation of test and control sides will be determined by coin toss: heads = left side, tails = right side). After surgery, the patient will receive questionnaires assessing postoperative discomfort, separately for each operated side. Follow-up visits will be scheduled at 1 week and 2 weeks after the procedure. Measurements of the listed gingival parameters will be performed at 6 and 12 months postoperatively. Additionally, 12 months after surgery, a gingival biopsy (2.5 mm in diameter and 1 mm thick) will be collected for histological analysis.

Statistical analysis plan

The results will be presented using descriptive statistics such as means, standard deviations (SD), percentages, and frequencies. Baseline defect characteristics will be used to ensure test and control sides were similar. The analyzed metrics will be calculated as follows: (1) MRC = $\frac{GR_0 - GR_6}{GR_0} \times 100\%$ (after 6 months); MRC = $\frac{GR_0 - GR_{12}}{GR_0} \times 100\%$ (after 12 months), (2) recession reduction (GR red) = $GR_0 - GR_6$ (after 6 months); GR red = $GR_0 - GR_{12}$ (after 12 months), (3) CAL gain = $CAL_0 - CAL_6$ (after 6 months); CAL gain = $CAL_0 - CAL_{12}$ (after 12 months), (4) KTW gain = $KTW_6 - KTW_0$ (after 6 months); KTW gain = $KTW_{12} - KTW_0$ (after 12 months), and (5) GT gain = $GT_6 - GT_0$ (after 6 months); GT gain = $GT_{12} - GT_0$ (after 12 months). The normality of distribution of quantitative variables will be verified with the Shapiro–Wilk test. The primary outcome variable (MRC) will be tested for superiority by Student’s t-test. The secondary outcomes will be tested for side differences by Student’s t-test. If significant, the outcomes will be verified by repeated measures of variance, with subject as random effect used ANOVA approach. Pearson’s chi-squared test will be used for comparison of fractions and the agreement of variable class distribution between tests and controls. Statistical significance will be defined as p value < 0.05.

Benefits of the study

It is anticipated that the side on which the sCTG is positioned during the tunnel technique procedure will not affect the surgical outcome.

Risks of taking part in the study

Surgical treatment may cause pain, swelling, and bruising/hematomas of the gingiva and facial skin.

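### Graft orientation goes to the left or right side by an unrestricted coin toss and no planned analysis includes mouth side; the toss is valid, but a balanced list plus a side term would cheaply protect precision

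*Combined protocol and SAP*

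**What the plan says.** The protocol's description of the study calls it a "randomized split-mouth interventional study" in 20 patients, each contributing one test and one control side. The procedure description gives the whole allocation rule: "Allocation of test and control sides will be determined by coin toss: heads = left side, tails = right side". It mentions no block, list or balance rule. It also leaves open whether the toss places the test or the control graft on the named side, although the probabilities below are the same either way.

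In the statistical analysis plan, "The primary outcome variable (MRC) will be tested for superiority by Student’s t-test". For the other endpoints, "The secondary outcomes will be tested for side differences by Student’s t-test". The SAP elsewhere speaks of test and control sides, so this phrase reads as test against control rather than left against right. Only after a significant result does the plan add "repeated measures of variance, with subject as random effect used ANOVA approach". Subject is the only term named there besides the comparison itself. The baseline check also compares test with control. Mouth side is known for every patient from the toss but is not used.

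**The concern.** A split-mouth trial with two layouts (test on left, test on right) has the structure of a two-sequence crossover, with mouth side in the place of period. Pairing removes what the two sides of one mouth share. It does not remove a left-right difference, which enters each test-minus-control difference with a plus or a minus sign according to the toss. If such a difference exists, it acts as extra noise in the comparison. When the draw is uneven, it also moves that particular trial's estimate.

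This matters because the trial is small and documents no effect size, SD or power, so no spare precision can be assumed. The protocol also anticipates that orientation will make no difference. Avoidable noise makes a non-significant result both more likely and less informative.

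**Working it through.** **Inputs from the documents.** 20 patients with one test and one control side each (description of the study); a coin toss for allocation (procedure description), taken as one fair toss per patient; significance level 0.05 (SAP), taken as two-sided because sidedness is not stated.

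**Assumptions.** The documents give no effect size, SD, power or left-right difference, so there is no planning figure to reproduce. The unit is the SD of the within-patient difference from all sources other than mouth side. The true effect is set at 0.66 SD, which 20 pairs detect with 80% power in a paired t-test. L is the left-minus-right difference in outcome unrelated to the graft, taken from 0 to 0.75 SD.

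**Step 1: balance of the toss.**
- P(10:10) = C(20,10)/2^20 = 184,756/1,048,576 = 17.6%.
- P(13:7 or worse) = 26.3% and P(14:6 or worse) = 11.5%, both exact two-tailed binomial.

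**Step 2: what L does.** Write d_i = τ + s_i·L + e_i, where d_i is test minus control, τ the orientation effect, and s_i = +1 if test is on the left and −1 if on the right.
- Over tosses, s_i has mean 0 and variance 1, so Var(d) = 1 + L² in SD units. That is 1.06, 1.25 and 1.56 at L = 0.25, 0.5 and 0.75.
- Given k patients with test on the left, the mean of s_i is 2k/20 − 1, so the estimate shifts by L(2k/20 − 1). At k = 14 this is 0.4L. As an illustration, with an assumed SD of 15 percentage points of MRC and L = 7.5 points, the shift is 0.4 × 7.5 = 3.0 points.
- Averaged over tosses the shift is zero.

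**Step 3: operating characteristics** (200,000 simulated trials per setting, paired t-test on 19 df without the side term, regression on s_i with 18 df with it).

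| L (SD) | Power: toss, no side term | Power: 10:10 plus side term | False positives without term: all draws | 14:6 or worse | All other draws |
|---|---|---|---|---|---|
| 0 | 80% | 79.8% | 5% | 5% | 5% |
| 0.25 | 78% | 80% | 5% | 7% | 4.8% |
| 0.5 | 71% | 80% | 5% | 12% | 4.0% |
| 0.75 | 61% | 80% | 5% | 18% | 3.3% |

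The last two columns recombine to the nominal level. At L = 0.5, for example, 0.115 × 12% + 0.885 × 4.0% = 4.9%. With the side term the false-positive rate is about 5% in every draw checked.

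**Step 4: which part of the remedy does the work.**
- At L = 0.5 SD, forcing 10:10 without the term gives only 72% power, with a false-positive rate of about 2.9%. The shift is gone, but L² is still in the error.
- Adding the term to coin-toss data gives about 77.5% power whatever L is. Without the term, power is 79.9% at L = 0 and about 78% at L = 0.25. The term therefore costs about 2.4 points if L = 0 and breaks even near 0.25 SD.
- The two together give about 80% at every L.

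**The case against.** The strongest reply is that the harm rests on a quantity the documents never mention. Nothing in them suggests that left and right heal differently, and the larger losses need L of 0.5 to 0.75 SD. That is about 76% to 114% of the assumed treatment effect (0.5/0.66 and 0.75/0.66). At 0.25 SD the loss is about two points of power. This stands, and it limits the priority of the point.

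A reader might infer that the coin toss biases the trial or inflates its type I error. The documents do not support that. An independent toss is proper randomisation, so the estimate is unbiased and the level is about 5% over all draws. The 7%, 12% and 18% rates belong only to the 11.5% of draws at 14:6 or worse, and the remaining draws are conservative. The shift in the estimate is conditional on the draw that occurs.

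The power figures presume a paired test, whereas the SAP says only Student's t-test. If the test is unpaired, these figures do not apply, although mouth side would still be ignored: each side carries ±L/2, so L²/4 is added to the variance within each arm. The unstated pairing is a separate and larger gap.

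Finally, a fixed 10:10 list lets anyone keeping count guess the last assignments. That is a real cost, which concealment reduces but does not abolish.

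**Conclusion.** The point holds as a cheap improvement in efficiency, not as an error that invalidates the trial. The allocation is unrestricted and mouth side is absent from every planned analysis. If a left-right difference exists, the trial loses precision, and an uneven draw shifts that trial's estimate by L(2k/20 − 1). The loss is small at L of 0.25 SD or less (80% to about 78% power) and material from about 0.5 SD (71%, then 61% at 0.75 SD). These sizes rest on an assumed L, an assumed true effect of 0.66 SD, a two-sided 5% level and a paired analysis. The documents state none of these except the 5% level.

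**What to change.** Make two changes together.

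1. Replace the toss with a pre-generated, concealed random list holding exactly 10 test-left and 10 test-right assignments, and state which graft the assignment places on the named side.
2. Specify the analysis as within-patient and include mouth side (left/right) as a fixed term for the primary and secondary outcomes. Equivalently, estimate the orientation effect as the simple average of the mean test-minus-control difference in the test-left patients and in the test-right patients, with a pooled error on 18 df.

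The cost is one line in the allocation paragraph, one model term, one degree of freedom (80.0% to 79.8% power if L = 0) and some predictability of the last assignments.

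If patients have already been tossed, the side term alone is optional. It protects against an uneven draw and a sizeable L, but gives up about 2.4 points of power if L is zero. Choose it as the primary analysis or as a sensitivity analysis, and record that choice before outcomes are seen.

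### No outcome is adjusted for its baseline value, so a chance imbalance between sides carries into the gain-score contrasts and precision is usually lost for GR red, KTW and GT

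*Combined protocol and SAP*

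**What the plan says.** The trial is described as a "randomized split-mouth interventional study" in 20 patients, each contributing one test and one control side. The Procedure description sets the randomisation: "Allocation of test and control sides will be determined by coin toss: heads = left side, tails = right side". No balancing on defect size is described.

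Before surgery the plan records "probing depth, height and width of gingival recession, gingival thickness (1 mm from the gingival margin), and width of keratinized gingiva". It repeats these later: "Measurements of the listed gingival parameters will be performed at 6 and 12 months postoperatively".

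The Statistical analysis plan gives baseline data one stated purpose: "Baseline defect characteristics will be used to ensure test and control sides were similar". It does not say how similarity is judged or what follows if the sides differ. Baseline values also enter the outcome formulas. MRC is a percentage change divided by GR0, whereas GR red, CAL gain, KTW gain and GT gain are plain differences from baseline. MRC goes to Student's t-test, and for the rest "The secondary outcomes will be tested for side differences by" the same test. The only model is a repeated-measures ANOVA with subject as a random effect. It is run only after a significant result and names no baseline covariate. Fractions are compared by chi-squared.

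**The concern.** Split-mouth pairing removes differences between patients, but not differences between the two sides of one mouth. If the coin happens to put the deeper recessions mostly on one side, that side has more recession to lose and will tend to show the larger reduction in millimetres. A similarity check can describe such an imbalance but cannot prevent or correct it, and nothing later in the analysis does so.

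Two things are at stake: the accuracy of the side contrast given the imbalance that actually arises, and the precision of a trial with only 20 pairs and no stated power calculation. The covariates that would help are already being measured.

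**Working it through.** The plan has no figure to reproduce: the 20 patients are given without effect size, SD or power.

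**Inputs.** From the documents: n = 20 pairs, coin-toss allocation, the outcome formulas, and a significance level of 0.05. Assumed: a paired, two-sided test (the plan says only Student's t-test); equal SDs of the baseline and follow-up side differences; and r, the correlation between those two side differences, which the documents do not give.

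**1. Size of a chance imbalance.** Let SD be the standard deviation of the within-patient baseline differences, test minus control.
- Standard error of their mean: 1/√20 = 0.224 SD.
- Range holding 95% of trials: ±1.96 × 0.224 = ±0.44 SD.
- If similarity were judged by a paired t-test at 5% (the plan does not say so), the largest non-significant difference would be 2.093/√20 = 0.47 SD.

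**2. Carry-over into a gain score.** With no treatment effect, the expected follow-up side difference is r times the baseline one. The gain-score contrast therefore moves by (1 − r) times the imbalance. At 0.44 SD this is 0.44 SD for r = 0, 0.22 SD for r = 0.5 and 0.09 SD for r = 0.8.

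A simulation with no treatment effect (40,000 trials per r, 20 pairs) gave these type I error rates:

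| r | Gain score, all trials | Gain score, imbalance above 1 SE | Adjusted, imbalance above 1 SE |
|---|---|---|---|
| 0 | 5.1% | 12.4% | 5.1% |
| 0.2 | 5.0% | 10.8% | 5.2% |
| 0.5 | 5.1% | 9.0% | 5.0% |
| 0.8 | 4.9% | 6.5% | 4.8% |

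**3. Precision for KTW and GT gain.** The gain-score variance is proportional to 2(1 − r). Regressing the follow-up side difference on the baseline side difference gives (1 − r²) × [1 + 1/(n − 3)]. The ratio is (1 + r)/2 × (1 + 1/17) = (1 + r)/2 × 1.059.

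| r | Variance ratio | Equivalent patients, 20/ratio | Power where the gain-score test has 80% |
|---|---|---|---|
| 0.3 | 0.65 × 1.059 = 0.69 | 29 | 92% |
| 0.5 | 0.75 × 1.059 = 0.79 | 25 | 88% |
| 0.7 | 0.85 × 1.059 = 0.90 | 22 | 84% |
| 0.9 | 0.95 × 1.059 = 1.01 | 20 | 79.5% |

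**4. GR red in millimetres.** Assume coverage is a constant 85% of the starting defect and the SD of paired GR0 differences is 1 mm.
- 1-SE imbalance: 0.85 × 0.224 × 1 = 0.19 mm.
- Edge of non-significance: 0.85 × 0.47 × 1 = 0.40 mm.

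Both figures scale with the SD: halving it to 0.5 mm halves them to about 0.10 and 0.20 mm. At complete coverage and an SD of 1 mm they would be 0.22 and 0.47 mm.

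**5. The primary MRC.** Under the same constant-share assumption MRC is 85% on both sides whatever GR0 is, so the spurious MRC difference is zero. If coverage is not a constant share, MRC can depend on GR0 in either direction. An illustrative simulation (20,000 trials per scenario; assumed baseline recession mean 3 mm, SD 1 mm, between-side correlation 0.5; five assumed relations of residual to baseline recession) gave adjusted/unadjusted variance ratios for MRC from 0.73 to 1.05.

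**The case against.** The strongest defence is that the planned tests are valid. The coin toss makes the unadjusted contrast unbiased over randomisations, pairing (if used) removes patient-level variation, and the overall error rate is about 5%. That stands. What remains is bias conditional on the observed imbalance, plus a loss of efficiency.

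Four stronger readings are tempting, and the documents do not support them.
- A reader might infer that every outcome is a raw gain score. The primary MRC is already scaled by GR0, and fractions are tested by chi-squared. Scaling is not covariate adjustment, but it removes the simplest route by which GR0 could distort the primary result.
- A reader might carry the 0.40 mm figure over to the primary test. It applies to GR red only. It is also an edge value resting on a similarity test the plan does not specify.
- A reader might take adjustment as a guaranteed gain. With 20 pairs the gain disappears near r = 0.9, and for MRC it can be a small loss.
- A reader might treat the similarity check as a decision rule. The plan attaches no exclusion or change of method to it, so the complaint about ensuring similarity is partly one of wording.

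The repeated-measures ANOVA does not close the gap, because it is conditional on significance and names no baseline covariate.

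**Conclusion.** The point holds as a low-cost improvement, not as a flaw that invalidates the trial. No outcome is baseline-adjusted, and the similarity check cannot make up for that. For KTW and GT gain, adjustment would be worth about 29, 25 or 22 patients' worth of gain-score data from 20 patients at r = 0.3, 0.5 or 0.7. For GR red, a chance imbalance of ordinary size could move the contrast by roughly 0.2 mm under the stated assumptions. For MRC no benefit can be promised.

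All values of r, SD and coverage are assumptions. The variance ratios describe a paired analysis; if the planned t-test is unpaired, they do not describe the comparison the trial would actually run.

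**What to change.** 1. State that baseline values will be reported descriptively by side, and drop the wording about ensuring similarity.
2. For 12-month recession in mm, KTW and GT, prespecify a paired ANCOVA: regress the within-patient side difference at follow-up on the within-patient side difference at baseline, taking the intercept as the adjusted side effect. An equivalent mixed model has side, same-side baseline and random patient, and must separate the within- and between-patient baseline slopes (for example by adding the patient's mean baseline value). Without that separation the slopes can blend, and the gains shown above are not derived for such a model.
3. Report each adjusted side difference with its 95% CI.
4. For MRC, add the GR0-adjusted paired analysis as a sensitivity analysis.

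The cost is SAP text and one degree of freedom (18 instead of 19). There is a slight loss of precision if r is about 0.9 or higher. No new data are needed, because recession, KTW and GT are already measured on both sides before surgery and at follow-up.

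### The SAP for this split-mouth trial does not commit to a paired analysis: the t-test is not stated to be paired, the patient enters only in a conditional later step, and fractions get an independent-samples test

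*Combined protocol and SAP*

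**What the plan says.** Under Description of the study, the trial is a "randomized split-mouth interventional study" and its size is given as "20 test sites and 20 control sites (20 patients". The Procedure description adds: "Allocation of test and control sides will be determined by coin toss". Both graft orientations are therefore used in every patient.

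The Statistical analysis plan section then states, for the primary outcome, mean root coverage: "The primary outcome variable (MRC) will be tested for superiority by Student’s t-test". For the others: "The secondary outcomes will be tested for side differences by Student’s t-test". The patient is mentioned once, in the next sentence: "If significant, the outcomes will be verified by repeated measures of variance, with subject as random effect used ANOVA approach". For categorical data: "Pearson’s chi-squared test will be used for comparison of fractions and the agreement of variable class distribution between tests and controls". The threshold is set by "Statistical significance will be defined as p value < 0.05", with no statement of one- or two-sided testing.

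The words paired, unpaired and independent do not appear. No confidence intervals are planned. No power, effect size, standard deviation or within-patient correlation is given.

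**The concern.** A split-mouth design pays off because healing capacity, tissue type, oral hygiene and other patient characteristics affect both sides and cancel in the within-patient difference. An analysis that ignores the pairing puts this variation back into the error term.

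Three features of the SAP leave that possibility open:

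- The name of the t-test covers both the paired and the two-sample form.
- The one analysis that explicitly contains the patient is conditional on significance.
- The one test whose form is unambiguous, Pearson's chi-squared, is an independent-samples test applied to the two sides of the same mouths.

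The direction of the possible error matters here. The Benefits of the study section expects graft orientation to make no difference to the result. A test that misses real differences pushes the trial towards that answer, and a non-significant result could easily be read as confirming it. With 20 patients and no stated power calculation, there is little precision to spare.

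**Working it through.** **Is there a figure to reproduce?** No. The sample size of 20 patients comes without the inputs that would generate it, so the check is of the test and not of the sample size.

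**Inputs from the document.** n = 20 pairs; significance level 0.05.

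**Assumptions, because the document is silent.** Two-sided testing; one value per side per patient; no dropout; normal outcomes with equal SD on the two sides (set to 1); within-patient correlation rho of 0, 0.3, 0.5 and 0.7.

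**Step 1: standard errors.** The mean difference has true standard error sqrt(2(1 − rho)/20). An unpaired test estimates it as about sqrt(2/20) = 0.316 whatever rho is. The true values are 0.316, 0.265, 0.224 and 0.173 at rho = 0, 0.3, 0.5 and 0.7. For positive rho, the unpaired standard error is too large by a factor of 1/sqrt(1 − rho).

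**Step 2: reference effect.** The critical values are 2.093 (paired, 19 df) and 2.024 (unpaired, 38 df). From the noncentral t with 19 df, 80% paired power needs a mean difference of 0.66 SDs of the difference. In SDs of one side this is 0.66 × sqrt(2(1 − rho)), which gives 0.93, 0.78, 0.66 and 0.51.

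**Step 3: apply both tests to the same simulated trials** (one million per correlation). The last column requires significance first in the unpaired test and then in a within-patient test, which mimics the conditional ANOVA.

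| Assumed rho | Difference (SD of one side) | Type I error, unpaired | Power, paired | Power, unpaired | Power, unpaired then within-patient |
|---|---|---|---|---|---|
| 0 | 0.93 | 5.0% | 80% | 82% | 78% |
| 0.3 | 0.78 | 2.1% | 80% | 70% | 70% |
| 0.5 | 0.66 | 0.75% | 80% | 54% | 54% |
| 0.7 | 0.51 | 0.1% | 80% | 27% | 26% |

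The paired test holds its type I error at about 5% in every row.

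**Step 4: can the ANOVA rescue the result?** No. A step that runs only after a significant first test can confirm or withdraw a finding, but it cannot add one. The last column never exceeds the unpaired power.

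**Step 5: what does the ANOVA imply about the first test?** With one value per side at a single visit, a repeated-measures ANOVA with patient as random effect is the paired t-test (F = t²). It would verify nothing if the first test were already paired. It adds information only if the first test ignored the patient, or if the ANOVA spans several visits. The SAP says neither.

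**The case against.** The strongest reply is that the plan never calls the t-test unpaired. Its name covers both forms, the text speaks of differences between sides, and the authors clearly know that each patient supplies both. The ANOVA need not be redundant either: every metric is defined at 6 and 12 months, so a paired test at each visit followed by a model over side and visit is a coherent reading.

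That much stands. A reader might infer that the SAP prescribes an unpaired test and treats the data as 40 independent units. The document does not say so. Two further inferences also fail:

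- **That the planned intervals are wrong.** None are planned.
- **That false positives are inflated.** Under positive correlation, an unpaired test gives fewer than 5% false positives. The harm is lost power.

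The size of the effect is also doubly conditional: on the test being run unpaired, and on a correlation that the document does not give. At rho = 0 nothing is lost. The simulation uses normal outcomes, whereas MRC cannot exceed 100%, so its figures are illustrative.

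The reply does not remove the point. If two analysts can follow the same text and obtain different primary p-values, the primary test is not pre-specified. Pearson's chi-squared is named outright and does not fit paired sides. The only explicit patient-level model is conditional on any reading.

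**Conclusion.** The concern holds in this form: the design is paired, and the SAP does not commit to an analysis that respects it. For the continuous outcomes this is an unresolved ambiguity, with the patient-level model placed behind a significance condition. For fractions it is a mismatch in the stated method.

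If the t-test is run unpaired, 80% power falls to about 70%, 54% and 27% at correlations of 0.3, 0.5 and 0.7, with no loss at zero. These figures rest on 20 complete pairs, one value per side, normal outcomes, two-sided testing at 0.05 and correlations chosen for illustration. If the t-test is in fact meant to be paired, there is no power loss for the continuous outcomes. The wording still has to say so, and the chi-squared problem remains. Because the ambiguity determines the primary p-value, it should be settled before the data are analysed.

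**What to change.** Change the Statistical analysis plan as follows.

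1. **Primary analysis.** Define it as the within-patient difference in MRC, test side minus control side. Test it with a two-sided paired t-test, or fit a linear mixed model with side as fixed and patient as random effect, and report it with a 95% CI. The two coincide with one value per side and complete pairs, so state that each side contributes one value and how several recessions on a side are combined into it. Name the visit to which the primary test applies, since MRC is defined at both 6 and 12 months.
2. **Continuous secondary outcomes.** Use the same within-patient analysis.
3. **Conditional step.** Delete the significance condition on the model with patient as random effect. If a model over both visits is wanted, specify it in its own right.
4. **Distribution check.** Apply Shapiro–Wilk to the within-patient differences. Because MRC has a ceiling, add a sign-flip permutation test as a sensitivity analysis. It mirrors the coin-toss allocation, under which the sign of each patient's difference is arbitrary if orientation has no effect.
5. **Fractions.** Replace Pearson's chi-squared with a paired method for test-versus-control comparisons: McNemar's test for two-category outcomes, and a paired counterpart where there are more categories.

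The cost is SAP wording only. No further patients, visits or measurements are needed.

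### Four to eight secondary t-tests are each judged at an unadjusted p < 0.05, with no testing order, adjustment or exploratory label

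*Combined protocol and SAP*

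**What the plan says.** Under Study endpoints the primary endpoint is "gingival recession/root coverage" and the secondary endpoints are "gingival thickness, width of keratinized gingiva". The Procedure description fixes two assessment times: "Measurements of the listed gingival parameters will be performed at 6 and 12 months postoperatively".

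The Statistical analysis plan defines five metrics, each at both visits: MRC, recession reduction (GR red), CAL gain, KTW gain and GT gain. Only MRC is singled out: "The primary outcome variable (MRC) will be tested for superiority by Student’s t-test". For the others the plan says "The secondary outcomes will be tested for side differences by Student’s t-test", and then "If significant, the outcomes will be verified by repeated measures of variance, with subject as random effect used ANOVA approach". Chi-squared tests on fractions and class distributions are added without a list. The decision rule for everything is "Statistical significance will be defined as p value < 0.05".

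The document contains no multiplicity adjustment, testing order, decisive visit for the secondary outcomes or exploratory label.

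**The concern.** When several tests are each judged at 0.05, the chance that at least one is significant by luck exceeds 0.05. That is acceptable for secondary outcomes if the plan says that they are descriptive or exploratory, or limits in advance which of them can support a claim. This plan does neither, so any one secondary result below 0.05, at either visit, may be reported as a significant difference between graft orientations.

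This matters here because the Benefits section expects orientation to make no difference. To the extent that this is right, any significant secondary result is a false positive, and nothing in the plan limits how it may be presented. With 20 patients and a null or inconclusive MRC result, an isolated difference in thickness or keratinized width could easily become the message of the report.

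**Working it through.** The plan states no family-wise error rate and no power calculation, so there is no figure of its own to reproduce.

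**Inputs from the documents**
- Per-test threshold: 0.05. Sidedness is not stated; two-sided is assumed.
- Patients: 20, split-mouth, so 20 within-patient differences (19 df). No dropout is assumed.
- Visits: 2.
- Secondary outcomes: 2 by the protocol's endpoint list, or 4 by the SAP's metrics other than MRC.

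**Size of the family**
- Protocol reading: 2 × 2 = 4 tests.
- SAP reading: 4 × 2 = 8 tests.
- The chi-squared comparisons are not counted, because their number is not given.

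**Independent tests**, P(at least one false positive) = 1 − (1 − 0.05)^m
- m = 4: 1 − 0.95⁴ = 18.5%.
- m = 8: 1 − 0.95⁸ = 33.7%.
- Expected number of false positives: 4 × 0.05 = 0.20 and 8 × 0.05 = 0.40.

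**Correlated tests.** The documents give no correlations, so these are assumptions: 0 to 0.5 between outcomes and 0 to 0.9 between visits. Null trials of 20 within-patient differences were simulated. Each outcome was tested at each visit by a two-sided paired t-test at 0.05, and trials with at least one rejection were counted. In the gated columns, the side effect averaged over the two visits must also be significant for the same outcome. This is how an ANOVA that pools visits would act as a filter.

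| Visit correlation | 4 tests | 4 tests, gated | 8 tests | 8 tests, gated |
|---|---|---|---|---|
| 0 | 17–19% | about 6% | 29–34% | 10–12% |
| 0.5 | 16–18% | about 8% | 27–32% | 13–16% |
| 0.8 | 14–15% | about 9% | 24–28% | 15–18% |
| 0.9 | about 13–14% | about 9% | 22–26% | 16–18% |

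The range within a cell comes from the correlation between outcomes. In a more extreme case, a common correlation of 0.9 among all tests, the ungated rates are still 9.4% for four tests and 12.4% for eight.

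**ANOVA run visit by visit.** With two sides per patient, one gain per side and patient as random effect, the F statistic for side is n·d̄²/s_d² on 1 and 19 df. Here d̄ and s_d are the mean and standard deviation of the within-patient differences. That is the square of the paired t statistic, so the p-value is the same and no false positive is removed.

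**Unpaired form.** The SAP does not say whether the t-test is paired. If it were unpaired and the two sides of a patient correlated at an assumed 0.5, the ungated rates would be about 2–3% for four tests and 4–6% for eight. With no correlation between sides they match the paired rates.

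**Effect of a restricted confirmatory set.** For two independent tests, 1 − 0.95² = 9.75% unadjusted, and 1 − 0.975² = 4.9% at 0.05/2 = 0.025 each. Power cost: a standardized paired effect of 0.66 has noncentrality 0.66 × √20 = 2.95. That gives 80% power at 0.05 and about 70% at 0.025.

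**The case against.** The strongest reply is that this is a small trial with one named primary variable, and that secondary results without adjustment are common and harmless when read as supportive. That is fair, and it is why a label would be enough. But the label is absent.

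Three stronger readings are tempting, and the documents do not support them.

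- **That there are at least eight tests.** The protocol names two secondary endpoints, so four is the minimum. Eight requires counting GR red and CAL gain, which the SAP lists only as analysed metrics. GR red is the numerator of MRC and fits the wording of the primary endpoint; CAL is not a named endpoint.
- **That a false-positive secondary is likely, or occurs one time in four under the plan as written.** Even eight independent tests give about one in three, so no false positive is the more probable outcome in every case computed. A figure of one in four fits eight paired tests at moderate correlation only if the ANOVA filters nothing. The plan does not say whether a t-test result is withdrawn when the ANOVA is not significant.
- **That "If significant, the outcomes will be verified by repeated measures of variance" shows confirmatory intent.** The SAP uses the same verb for the Shapiro–Wilk check, so it may mean no more than checked. The step can equally be read as allowing for two sides within one patient.

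It is also true that inflation above 5% is not guaranteed for an unpaired test. That protection would come from ignoring the pairing in a split-mouth trial, which is not a multiplicity plan. Finally, the no-effect expectation is in the Benefits section while the SAP tests superiority, so the null is a scenario here and not an established fact.

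**Conclusion.** The point holds as a gap with a measurable consequence. Under the stated rule, with paired tests, 20 complete pairs and no true effect, at least one secondary outcome is falsely significant in about 13–19% of trials with four tests and 22–34% with eight. If the ANOVA pools visits and acts as a strict gate, the rates are about 6–9% and 10–18%, still above 5%. If it is run per visit, the ungated rates stand.

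These figures rest on assumed correlations, on the paired form and on two-sided testing, none of which the documents state. They do not include the chi-squared comparisons. The MRC test is not affected, so this is an inexpensive improvement to what may be concluded from the secondary results and not a threat to the main analysis.

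**What to change.** **Simplest change.** Replace the sentence on secondary outcomes with one stating that all secondary comparisons are exploratory, and that they will be reported as within-patient differences with 95% confidence intervals and without claims of significance.

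**If the sponsor wants confirmatory secondary claims.** Name GT gain and KTW gain, the two endpoints that the protocol lists, at one visit chosen in advance (12 months, for example). Test them with Holm's procedure at a family-wise two-sided 0.05. Label everything else exploratory: GT and KTW gain at the other visit, GR red and CAL gain at both visits, and the comparisons of fractions and classes. The visit and the procedure are the sponsor's choice; what matters is that the set is small and fixed before the data are seen.

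**Cost.** SAP wording only, with no added patients, visits or measurements. Secondary results outside the named set can no longer be called significant. Under the second option, the first Holm step at 0.025 lowers power from 80% to about 70% for an effect that has 80% power at 0.05; the fully exploratory option avoids this.
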